- All procedures will occur in the Dermatology clinic at the Sacramento VA Medical Center (observed by [name], [name], and/or [name]), three times per week for three consecutive weeks for total of nine study visits. Subjects will be counseled regarding common expected procedure outcomes including warmth, erythema (redness) and edema (swelling), found to resolve within 24 hours in other studies. (Sadick 2008) Any adverse events that occur in office during or immediately after HF-LED-RL phototherapy or mock therapy session will be recorded by [name]. Subjects will be called on Mondays to serve as a reminder of upcoming study visits for the week.
- Subjects will record daily any adverse events that occur at home using a subject diary of adverse events. The study diary will be completed approximately every 24 hours from the time of completion of the study procedure. The subject diary will have instructions on the first page and a

chart on other pages for the subject to complete for every symptom noted at home (attached as separate document). The chart will have headers of 'Date,' 'Time Symptom Started,' 'Time Symptom Cleared,' 'Location,' 'Describe the Symptom,' 'Severity,' 'Things that Make it Better,' 'Things that Make it Worse,' 'Any Treatments Tried at Home,' and 'MD Initial'. If a subject notices any changes sooner than 24 hours, they are encouraged to note it in their subject diary as soon as possible. If there are no changes, subjects will write "There are no changes." Recording in a diary should take 0 minutes per day if there is no reportable change. It may take up to 3 minutes per day if there is a reportable change. If there are any reportable changes, subjects will describe reportable changes using the provided instructions and template. Prior to study procedure at every study visit, subjects will be asked about any adverse events that have occurred, including, but not limited to: erythema, blisters, swelling, pain, ulceration, infection, numbness, tingling, and weakness. Subject's diaries will also be reviewed prior to study procedure at every study visit. [name], [name], or [name] will initial in the 'MD Initial' area at every visit, certifying that one of the researchers has reviewed the subject diary at every study visit.

Study Timeline:

HF-LED-RL Phototherapy or mock therapy procedure times are as follows:

Group 1 (480 J/cm²; 3 or 6 HF-LED-RL phototherapy subjects and 2 or 4 mock therapy subjects) - 90 minutes

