5.2 Recruitment Methods

- The total number of participants approved for recruitment is 200.
- Potential subjects will be identified and recruited from the Sacramento VA Medical Center, Mather via discussion with [name], [name], and/or [name] in Dermatology Clinic or through subject interest from IRB-approved flyers posted at the Sacramento VA Medical Center.
- Flyer (Please see below and as separate attachment)

Inviting Veterans to Participate in a Clinical Trial Studying the Safety of Red Light On Skin!

The Dermatology Service is exploring the safety of a FDA-cleared red light device. To study the safety of red light, we are evaluating different treatment times using the device in healthy skin over a three-week period. We previously studied the safety of light in all skin types and this study is designed to investigate the effects of light on fair skinned individuals.

Would you like to:

- Help veterans and the population at large?
- Make a contribution to medical science?
- Help discover new treatments for skin disease?
- Get compensated for your time participating in this study?

PLEASE ASK US!

Who may participate?

- Veterans of any age, with Caucasian (white) skin that may burn easily.
- Veterans who have not participated in a Sacramento VA red light study previously.
- Veterans wanting to make a positive impact on others.

Where is this study?

- Building 801, Dermatology Clinic, Sacramento VA Medical Center, Mather

If you are interested in participating in this study or if you have any questions, please contact research coordinator:

[name]
[contact]

- Subjects will receive a prorated amount of compensation based upon the number of completed study visits. Subjects must complete two or three study visits in the week to receive payment for that week. If patients complete two study visits in a week, they will receive a prorated payment of \$33.33 for that week. If a subject completes three study visits in a week, they will receive a payment of \$50 for that week. Completion of week 1: \$50, week 2: \$50, and week 3: \$50. Patients will receive a check weekly and there will be no delay in receiving the payment. If a subject misses two or more study visits total, he/she will be discontinued from the study.

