5.7 Withdrawal of Subjects

- Subjects may be withdrawn from the research without their consent in the event of an adverse event that jeopardizes the subject's safety or subject's noncompliance (e.g. missing two or more study visits). In the event that subject's study participation has to be discontinued, the principal investigator will explain to the participant the reasons for termination.
- There are no consequences/penalties should a subject decide to withdraw from the research. The subject is encouraged to contact [name] for the end-of-study visit. End-of-study visit will include photograph of the treated forearm, physical examination of the treated forearm, and collection of the subject's study diary. Subjects will be instructed to notify their primary care physician or follow-up in Dermatology clinic if any questions or concerns arise after the end of the study.

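### A subject who misses two visits leaves the trial with no staff-led adverse event enquiry required, so a reaction that caused the absence can go unrecorded; sections 5.2 and 5.7 also conflict

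*Combined protocol and SAP*

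**What the plan says.** **The missed-visit rule.** Section 5.2 states: "If a subject misses two or more study visits total, he/she will be discontinued from the study". Section 5.7 says only that subjects may be withdrawn, and gives as one ground "subject's noncompliance (e.g. missing two or more study visits"). It lists an adverse event that jeopardizes safety as a separate ground. Neither section makes the outcome depend on the reason for the absence.

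**How home events reach the study.** Section 5.1: "Subjects will record daily any adverse events that occur at home using a subject diary of adverse events". The same section has staff ask about adverse events and review the diary before the procedure at every study visit, and section 6.0 also places monitoring at study visits. Section 5.5 requires subjects to keep the diary and report adverse events. Section 5.1 gives them contact details for the study team and commits to documenting all adverse events. The only scheduled call is described as follows: "Subjects will be called on Mondays to serve as a reminder of upcoming study visits for the week".

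**After discontinuation.** Section 5.7 says that "the principal investigator will explain to the participant the reasons for termination". On the final assessment it says: "The subject is encouraged to contact [name] for the end-of-study visit". The content is specified: "End-of-study visit will include photograph of the treated forearm, physical examination of the treated forearm, and collection of the subject's study diary".

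**Counting.** Section 5.6 does not say how discontinued subjects enter the adverse event frequency.

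**The concern.** The trial exists to establish safety, and adverse events drive every decision in it. The absence rule can end staff-led collection of that outcome for a reason related to the outcome itself. Take a subject who develops pain or a blister after a Friday session and skips Monday and Wednesday. Under section 5.2 this subject is discontinued before any staff member is required to ask about symptoms. From then on, a record depends largely on the subject taking the initiative.

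Section 5.1 lets single subjects decide the path. No event in the first five at 480 J/cm² means escalation, one means a repeat cohort, and two or more mean stopping. In Group 1A a single event stops the study. One unrecorded event can therefore turn a stop into a repeat, or a repeat into an escalation. The expansion claim is just as sensitive, because it rests on seeing no events at all.

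**Working it through.** **Inputs.** Section 5.1 gives 30 (or 33) HF-LED-RL subjects at the final dose, 95% confidence, a target rate below 0.10, and 3 HF-LED-RL subjects in a first escalation cohort. I read the 95% as a one-sided upper limit. The documents give no rate of dropout or of reaction-related absence.

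**1. The plan's own figure.** Rule of Three: n = 3/0.10 = 30. Exact limit with zero events: 1 − 0.05^(1/n). At n = 30 this is 1 − 0.05^(1/30) = 0.0950. The plan's number is reproduced, and the smallest n that meets the target exactly is 29.

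**2. Unassessed subjects left out of the denominator, zero events recorded.**

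| Assessed HF-LED-RL subjects | Exact upper limit | 3/n |
|---|---|---|
| 30 | 9.50% | 10.00% |
| 29 | 9.81% | 10.34% |
| 28 | 10.15% | 10.71% |
| 27 | 10.50% | 11.11% |

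On the exact limit, two unassessed subjects out of 30 defeat the claim. On the 3/n approximation that the plan cites, one does.

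**3. A hidden event counted as event-free.** With x events in n, the exact limit is the 0.95 quantile of Beta(x+1, n−x). For 1/30 this is Beta(2, 29), giving 0.1486. A reported 0/30 (9.5%) would then stand in place of 14.9%. For 1/33 the limit is 13.6%.

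**4. The total of 33.** This total arises when a repeat cohort was needed at the final dose, so one adverse event has already been recorded. If that event was in an HF-LED-RL subject, the limit is at least 13.6% and the claim has already failed. If it was in a mock subject, 33 − 29 = 4 HF-LED-RL subjects can be unassessed before the exact limit passes 10%.

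**5. Illustration with assumed hiding rates.** Let p be the true event rate and m the fraction of events hidden. The chance of no recorded event in n subjects is (1 − p(1−m))^n.

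| m | p = 10%, n = 30 | p = 30%, n = 3 |
|---|---|---|
| 0 | 0.90^30 = 4.2% | 0.70^3 = 34.3% |
| 0.25 | 0.925^30 = 9.6% | 0.775^3 = 46.5% |
| 0.5 | 0.95^30 = 21.5% | 0.85^3 = 61.4% |

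At a true rate of 10%, hiding a quarter of events roughly doubles the chance of a false zero. Both m and p are assumptions, because the documents give nothing from which to estimate them.

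**The case against.** The best defence is that several routes could still capture the event. Section 5.5 places a reporting duty on the subject that does not depend on attendance. Subjects have the team's contact details. The Monday call gives an opening, and so does the investigator's explanation of the termination. The end-of-study visit includes an examination and diary collection. If the two misses are not consecutive, the visit between them includes questioning, examination and diary review. The diary instructions are a separate attachment and the consent pages are not available here, and either may cover reporting or diary return.

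This rules out some stronger readings:

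- A reader might infer that no contact is required after discontinuation, or that events are learned of only if the subject attends. The documents do not support either. Section 5.7 commits the investigator to an explanation, and section 5.5 requires reporting.
- A reader might infer that the payment terms contradict the limit on absences, because "If patients complete two study visits in a week, they will receive a prorated payment of \$33.33 for that week". They do not. That is a weekly rate, and the same paragraph caps total misses.
- A reader might take the move from 9.5% to 14.9% as the effect of this rule. It is the cost of any single missed event, and it assumes that the discontinued subject is counted as event-free. Section 5.6 does not say so.
- A reader might expect the loss to be larger in the HF-LED-RL arm. Section 5.1 says those subjects may be at greater risk but says nothing about attendance, so this is only a possibility.

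The central point stands. The remaining routes rely on the subject's initiative, or are staff contacts with no adverse event question attached. None requires staff to ask about events or to retrieve the diary once a subject has stopped attending.

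**Conclusion.** The point holds. Sections 5.2 and 5.7 conflict on whether two missed visits lead to automatic or discretionary removal, and they must be reconciled. I take no position on which is right. Separately, the plan has no staff-initiated ascertainment after discontinuation and no counting rule for subjects who leave unassessed. An event that caused an absence can go unrecorded; it will not necessarily do so.

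The consequence is large for each subject affected. One hidden event can change a cohort decision. In a group of 30, either one hidden event counted as event-free (14.9%) or two unassessed HF-LED-RL subjects (10.15%) defeats the claim of a rate below 1 in 10. These limits assume exact one-sided 95% bounds. How often this would happen cannot be estimated from the documents. The change is worth making before enrolment because the decision rules have almost no margin and the remedy is cheap.

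**What to change.** 1. Reconcile sections 5.2 and 5.7 so that one rule on missed visits applies.
2. State that stopping sessions does not stop data collection.
3. At each missed visit, and after any discontinuation or withdrawal, have staff contact the subject, using the Monday call or the existing termination contact. They ask the adverse event questions already listed in section 5.1, record the reason for absence, and seek the diary.
4. Classify any reaction by the protocol's own adverse event definition. An absence caused by a reaction should not automatically become an adverse event, because sections 2.0 and 5.1 exclude erythema lasting less than 24 hours.
5. In section 5.6, state that subjects who cannot be assessed are not counted as event-free, either in cohort decisions or in the Rule of Three denominator. State in advance how a cohort with an unassessed subject is to be read.
6. Report a sensitivity count that treats unassessed HF-LED-RL subjects as events. With no other events, one such subject in 30 gives an upper limit of 14.9% and two give 19.5%.

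The cost is protocol wording, a few extra calls and some effort to retrieve diaries. The upper limit may also turn out less favourable than a count that treats everyone who left as event-free.

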5.3 Informed Consent Procedures

- Informed consent will be obtained using IRB-approved informed consent forms.
- Informed consent will be obtained by [name], [name], or [name]. No persons with impaired decision-making capacity will be recruited to this study. [name], [name], and/or [name] will determine whether the potential subject has decision-making capacity via conversational interaction with the potential subject.
- [name], [name], and [name] has completed the CITI Human Research Subject training and has the knowledge and understanding of the clinical trial to obtain and document informed consent and explain the study to the subjects.

5.4 Inclusion/Exclusion Criteria

Inclusion Criteria:

- 1) Healthy subjects, any sex, ethnicity, and age with Fitzpatrick skin types I, II, or III that do not meet exclusion criteria. Fitzpatrick skin types will be determined based on NIH's race/ethnicity categories. Fitzpatrick skin types I to III will be persons who are Caucasian or white. NIH defines "White" as "A person having origins in any of the original peoples of Europe, the Middle East, or North Africa." A subject's Fitzpatrick skin

type, whether they are Fitzpatrick skin type I or II or III, will not be documented.

- 2) Nondominant proximal anterior forearm is wide enough to ensure reproducible placement of HF-LED-RL phototherapy or mock therapy hand-held unit
- 3) Available and willing to attend all study visits
- 4) Able and willing to give informed consent

Exclusion Criteria:

- 1) Subjects with Fitzpatrick skin types IV, V, or VI
- 2) Subjects on any photosensitizing medications (e.g. lithium, melatonin, phenothiazine antipsychotics, antibiotics)
- 3) Subjects with light-sensitive conditions (Based on medical chart review, self-reporting, or failing the 20 minutes at fluence of 106.7 J/cm² photosensitivity evaluation)
- 4) Subjects with diabetes mellitus (DM) (Based on medical chart review or self-reporting). Subjects with DM may have a higher risk of longer wound healing time.
- 5) Subjects with a history of skin cancer: basal cell carcinoma (BCC), squamous cell carcinoma (SCC), or melanoma
- 6) Subjects with systemic lupus erythematosus (SLE)
- 7) Subjects with open wounds on the nondominant proximal anterior forearm
- 8) Subjects with fibrotic skin disease or other skin conditions on the nondominant proximal anterior forearm
- 9) Subjects with tattoos that cover the procedure site on the nondominant proximal anterior forearm
- 10) Subjects who previously participated in the Phase 1 study of LED-RL in Human Skin (VA file #15-12-00756)

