- Potential subjects who are willing and eligible for the study will be recruited from the Sacramento VA Medical Center, Mather. No vulnerable populations will be recruited to this study. Subjects with Fitzpatrick skin types IV, V, and VI will be excluded because the MTD for subjects with Fitzpatrick skin types IV, V, and VI was established in the “previous Phase 1 LED-RL study” as 320 J/cm² HF-LED-RL due to an adverse event of a blister in one study subject with Fitzpatrick skin type V at 480 J/cm² HF-LED-RL. No subsequent testing of 480 J/cm² was performed in subjects with Fitzpatrick skin types IV, V, and VI due to the study design of the “previous Phase 1 LED-RL study” where if any adverse event occurred, further testing at that dose would be discontinued. In this study, we will not test higher fluences of 480 J/cm² and 640 J/cm² in subjects with Fitzpatrick skin types IV, V, and VI. Subjects who have previously participated in the “previous Phase 1 LED-RL study” will be excluded to maintain unbiased results.

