5.6 Data Analysis

- Once all study subjects have finished all study procedures and data collection is complete, [name], [name], and/or [name] will then be performing the data analysis. Data analysis will include analysis of demographics (e.g. age, gender, ethnicity, race, Fitzpatrick skin type) in each cohort by HF-LED-RL or mock therapy dose, frequency of adverse events by HF-LED-RL or mock therapy

groups, mean duration of erythema, total duration of erythema, and subgroup analysis by demographics of adverse events. Self-reported outcomes of erythema duration are based on self-reporting from subject's diary.

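### Fitzpatrick type is assigned from race and not recorded, so the planned skin-type analysis has one constant label and a conclusion for types I to III strictly describes NIH-White subjects

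*Combined protocol and SAP*

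**What the plan says.** Inclusion criterion 1 in Section 5.4 gives the method of typing: "Fitzpatrick skin types will be determined based on NIH's race/ethnicity categories". It then maps race to type, "Fitzpatrick skin types I to III will be persons who are Caucasian or white", and takes the NIH definition of White, which rests on origin: "A person having origins in any of the original peoples of Europe, the Middle East, or North Africa". It adds that a subject's individual type, "whether they are Fitzpatrick skin type I or II or III, will not be documented".

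Exclusion criterion 1 bars "Subjects with Fitzpatrick skin types IV, V, or VI" and names no separate way to assess this. Section 2.0 states the intention behind it: "we will not test higher fluences of 480 J/cm² and 640 J/cm² in subjects with Fitzpatrick skin types IV, V, and VI".

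The Definitions and Table 1 classify type by how skin burns and tans, with a basic skin color beside each type, and present the link between white skin and types I to III as a general one.

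Section 5.6 plans "analysis of demographics (e.g. age, gender, ethnicity, race, Fitzpatrick skin type" and so on, by cohort, together with "subgroup analysis by demographics of adverse events".

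**The concern.** Skin type is the subject of this trial. It is in the title and the objective, and Section 2.0 says the results may establish differential safety by type and guide dose stratification in later studies. Yet the rule that assigns type asks nothing about burning, tanning or skin color. Three things are at stake:

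- whether the analysis by type promised in 5.6 can be done at all;
- whether exclusion 1 can detect the people it names;
- whether a result reported for types I to III describes the people who were treated.

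If an event occurs, it counts toward the repeat-cohort and stopping rules of Section 5.1 whatever the subject's type by Table 1. The data could not show whether it came from a type the trial meant to leave out.

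**Working it through.** **Reading the sections together**

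1. Analysis. Under 5.4 the Fitzpatrick variable has one level, I to III. One level gives zero contrasts. Race is close to constant for the same reason, because entry requires White. Age, gender and ethnicity can still vary. This step needs no assumption.
2. Entry. Table 1 gives type IV as skin that rarely or minimally burns and tans deeply. A person of European, Middle Eastern or North African origin with that response is labelled I to III by 5.4. Exclusion 1 has no other test, so it does not detect this person.
3. Population. All that is verified about a subject is race category, so the population described is NIH-White.

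**The plan's own figure**

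Section 5.1 uses the Rule of Three to claim, with 95% confidence, a risk below 1 in 10: 3/30 = 10.0%. The exact one-sided zero-event bound is 1 − 0.05^(1/n).

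| n on HF-LED-RL at the final dose | 3/n | Exact bound |
|---|---|---|
| 36 | 8.3% | 8.0% |
| 33 | 9.1% | 8.7% |
| 30 | 10.0% | 9.5% |
| 29 | 10.3% | 9.8% |
| 28 | 10.7% | 10.1% |

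The 30 is 3 + 27. The 36 assumes no events in Groups 1 and 2, so that ten subjects default to Group 3 and split 3:2: 3 + 27 + 6. The row for 33 needs care. If 33 is reached through a repeat cohort at that dose (6 + 27), an event has already occurred there, and the zero-event bound applies only if it was on mock. With 1 event in 33 on HF-LED-RL, the exact bound is 13.6%. A zero-event 33 can also arise if Group 1 was repeated and Group 2 was not: 3 + 27 + 3.

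**Does misclassification weaken the zero-event bound?**

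Let p be the event risk in types I to III, q the risk in type IV, and m the number of type IV subjects among n. Then P(0 events) = (1 − p)^(n−m) × (1 − q)^m. If q ≥ p, as Section 2.0 asserts, this is at most (1 − p)^n, so the full-n bound remains valid for p. Only if nothing is assumed about q must the m subjects be discarded. The bound then passes 10% at 28 remaining, which takes 2 misclassified of 30, 5 of 33 or 8 of 36.

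**How many could enter (illustration only)**

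The documents give no share of White volunteers who are type IV, so f below is assumed. If Group 3 is run, subjects receiving HF-LED-RL at 480 or 640 J/cm² number 3 + 3 + 27 = 33 to 6 + 6 + 27 = 39. Expected number = N × f; P(at least one) = 1 − (1 − f)^N.

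| Assumed f | Expected, N = 33 to 39 | P(at least one), N = 33 to 39 |
|---|---|---|
| 2% | 0.7 to 0.8 | 48.7% to 54.5% |
| 5% | 1.7 to 2.0 | 81.6% to 86.5% |
| 10% | 3.3 to 3.9 | 96.9% to 98.4% |
| 20% | 6.6 to 7.8 | above 99% |

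**The case against.** The race rule is a declared operational definition. The Abstract and Sections 2.0, 5.1 and 5.4 all use it, and it matches how the previous study assigned type, including the type V subject with the blister. Under that rule a White subject is not type IV, so exclusion 1 is breached only when Table 1 is applied. That stands, and it makes the entry issue one of measurement quality. It does not reconcile 5.4 with the Definitions or with 5.6.

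There is also partial mitigation. The flyer in 5.2 asks for skin that may burn easily, the test at 106.7 J/cm² uses the study light itself, and screening includes chart review and examination. These may reduce such entries, but none of them classifies type, and the flyer is not an eligibility criterion. Section 5.6 names skin type only as an example and attaches no test to it, so what is lost there is descriptive.

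A reader might infer more than the documents support:

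- *That type IV subjects face shown excess risk here.* No misclassification rate or type IV event rate is given.
- *That the zero-event bound fails.* On the protocol's own premise it holds. The margin of exactly 10.0% from the Rule of Three at n = 30 exists with no misclassification at all.
- *That recorded type should replace race as the entry rule.* This would open 480 and 640 J/cm² to non-White subjects scored I to III by sun response. It sits badly with Section 2.0, which classes those groups as IV to VI and attributes red-light sensitivity to melanin.

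**Conclusion.** The concern holds and should be fixed. The conflict between 5.4 and 5.6 is certain: one label, zero contrasts by skin type. It is equally certain that exclusion 1 cannot detect a White subject who is type IV by Table 1, and that the result describes NIH-White subjects. How many such subjects would enter is unknown; the shares of 2% to 20% are assumptions.

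The main losses are the empty skin-type analysis, the population label, and the inability to attribute any event to a type. The zero-event bound for types I to III is not among them, provided that type IV is at least as sensitive as I to III, as Section 2.0 asserts.

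**What to change.** In Section 5.4:

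- Delete the statement that type will not be documented. Record each subject's Fitzpatrick type (I to VI) at Visit 1 screening against Table 1, noting both sun response and basic skin color, in addition to NIH race.
- Keep the existing Caucasian/white requirement, so that eligibility is not widened to non-White subjects and comparison with the previous study's race-based typing is kept.
- State that exclusion 1 is checked against the recorded type, and reconcile the matching statement in Section 2.0 with this.
- State in advance how a disagreement between the two Table 1 columns is resolved.

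In Section 5.6, use the recorded type and label those summaries descriptive.

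The cost is a few screening questions and one data field at an existing visit, some self-report error, and some extra screen failures. Their number is unknown. To fill 65 places, 65/(1 − f) − 65 gives about 1, 3, 7 or 16 extra otherwise eligible volunteers at assumed shares of 2%, 5%, 10% or 20%. The total of about 66 to 81 is well within the 200 approved.

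If type will not be recorded, state the population and conclusion as NIH-White throughout: title, Abstract, Section 2.0, Objectives (3.0), Section 5.1 and Section 5.4. Say that types IV to VI are excluded through race only, and delete Fitzpatrick type from 5.6. This adds no recruitment but gives up any statement by skin type.
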